Aim 1: Efficacy. Using a randomized trial (N=328), we will test whether a lifestyle intervention delivered via an online social network (Get Social) will result in a mean percent weight loss at 12 months that is not appreciably worse than the gold-standard in-person group-based lifestyle intervention (Traditional), i.e., the social network arm will not lose on average 2% less than the in-person arm. Secondary non-inferiority outcomes include weight loss at 12 months, and dietary intake and physical activity at 6- and 12-months.

Aim 2. Cost Analyses. To determine whether the lifestyle intervention delivered via an online social network will cost less per participant than in-person delivery. We hypothesize that the Get Social condition will cost less per participant than the Traditional condition.

Aim 3. Predictors (exploratory). We will test predictors of weight loss in the Get Social condition including engagement, age, sociability, neuroticism, openness, and smartphone and social network use. We hypothesize that people who are younger, more sociable, engage more on the social network, higher in neuroticism/openness, and heavier overall smartphone and social network users will lose more weight in the Get Social condition.

For EACH Participant Population State the Number of Participants to be Enrolled and Screened, if applicable: [State the total number of participants to be enrolled and, if enrolling more than one participant population, describe the total enrollment for each. Tip: consider attrition and the number of participants who may fail screening. Use of a range may provide flexibility.] Note that the range must be justified in the **Justification of Sample Size section below**.

The total number of subjects that will be recruited will be 328 randomized participants and 6 interventionists. It is estimated that we will screen 700 participants to achieve this recruitment goal.

Justification of Sample Size: [For qualitative and pilot studies, describe how the proposed sample size is appropriate for achieving the anticipated results. For quantitative studies, provide a power analysis that includes effect size, power and

level of significance with references for how the sample size was determined. Explain the rate of attrition and possible number who fail the screening, with references as appropriate.]

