Participants will be withdrawn from the study if: they drop from participation, do not complete all baseline procedures, disrupt in-person groups, or post inappropriate content on Twitter. Participants reporting that they would like to withdraw from the study will be given the option to: 1) withdraw from all intervention-related activity and contacts, but still complete the final assessment or 2) withdraw from the study completely with no additional study contact. If a participant becomes pregnant during the study, they will be withdrawn from the intervention, but will be given the option still complete the follow-up assessments.

Potential Harms/Risks and Inconveniences: [Describe the potential risks to participants (and secondary participants, if applicable) and **steps taken to minimize risks** for each participant population. Assess the likelihood of the risk occurring and, if it were to occur, the seriousness to the participant. Types of risks to consider include, but are not limited to: physical, psychological, social, legal, employment, and financial. Also describe any anticipated inconveniences the participants may experience (time, abstention from food, etc.).]

Possible risks for being in this study includes: Injury while exercising, breach of confidential information, and discomfort completing measures. The attempt to avoid risks to participants will be addressed by: suggesting moderate intensity exercise to avoid discomfort, pain, or injury. Participants reporting discomfort will be referred to their PCP. Injuries are unlikely to occur since we screen out medical conditions that could make someone prone to injury, we obtain medical clearance, and we only suggest moderate activity. We also provide participants with information on exertion level and remind them to see medical attention if there is pain. Tracking data will be stored electronically in REDcap, a network secure data entry program; any data on paper will be stored in a locked file cabinet; and participants will be informed that they may withdraw from the study at any time if they feel discomfort with any of the study procedures.

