Attendance will be collected at all study visits. If a participant misses a group, materials will be sent to them and a make-up session will be offered. If a participant chooses to drop from the intervention, they will be given the option to skip the rest of the intervention visits, but still complete the final assessment. Compliance information (number/percent of intervention visits attended; engagement in Twitter private group) will be provided in a report to the safety officers.

Data Security:

The databases will be maintained on UConn and UMass servers where security will be maintained through access controls. The program director will control the database and surveys and will allow access to necessary staff. Staff wanting access to identifiable data will need to: have prior IRB approval to be on the project, apply for a REDCap account, be approved by the program directo, and utilize a password for login.

Data review (completeness/outliers):

Data reports will be reviewed by the data manager, project director, statistician, and PI. Reports will include completeness of data (visits completed, online engagement, % of expected forms submitted, % of submitted forms passing edit); missed visits and missing information within visits; descriptive information for each endpoint (change in weight and physical activity) without statistical testing; and quality control analyses for primary outcome (change in weight).

Privacy/Confidentiality Part 1: [Explain how the privacy interests of participants will be maintained during the study (note that **privacy pertains to the individual not to the data**). Describe how data will be coded. Do not use the any potentially identifiable information such as initials of participants as part of the code. If identifiable, sensitive information (illegal drug use, criminal activity, etc.) will be collected, state whether a Certificate of Confidentiality will be obtained. Be sure to state whether any limits to confidentiality exist and identify any external agencies (study sponsor, FDA, etc.) that will have access to the data. If participants will be screened, describe the plans for storage or destruction of identifiable data for those that failed the screening.]

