Linear multivariable models will be used to estimate change in daily caloric intake at 12 months; such models are reasonable given the target sample size and that changes in these outcomes are approximately normally distributed. We will examine the proportion of participants engaging in 150+ minutes/week of moderate/vigorous intensity physical activity (MVPA) using generalized estimating equations with a logit link function and incorporating repeated measures over time. For participants missing MVPA at either follow-up timepoint will use a baseline observation carried forward approach to impute their activity level (150+ vs <150 MVPA mins/week) at that timepoint. The distribution of secondary outcomes will be explored graphically and inform the primary outcome analysis; analyses will be modified as needed through transformation of the data.

Cost

We will calculate total intervention delivery costs per participant by treatment condition using time reported by intervention staff and convert to per-participant costs using national salary data from the Bureau of Labor Statistics. We will conduct sensitivity analyses to estimate a range of per-participant costs after varying the inputs (e.g., time spent conducting intervention, different intervention tasks, salary estimates). While we had originally aimed to examine costs for participants to participate in their respective intervention, we discovered methodologic challenges with collecting accurate and complete data from participants. As a result of what we learned, we have launched a separate study to develop methods for accurately collect participant time spent to participate in a social media delivered behavioral intervention. Without participant-level data, we are unable to conduct the analyses originally planned. Instead, we report the total intervention delivery costs per participant in both hours and dollars per participant for each of the two interventions.

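### Participants who stop the intervention before month 6 but agree to be followed are offered only the 12-month assessment, so their 6-month data go missing avoidably

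*Protocol*

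**What the plan says.** The Protocol (Inclusion/Exclusion Criteria, withdrawal paragraph) gives a participant who asks to leave two choices. The first is to "withdraw from all intervention-related activity and contacts, but still complete the final assessment". The second is to "withdraw from the study completely with no additional study contact". The Participant retention text under Data Safety Monitoring repeats the first choice for anyone dropping the intervention: "they will be given the option to skip the rest of the intervention visits, but still complete the final assessment".

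The same withdrawal paragraph treats pregnancy differently. Of those participants it says "they will be withdrawn from the intervention, but will be given the option still complete the follow-up assessments", in the plural.

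The Protocol's Study Design and Follow up sections schedule assessments at 6 and 12 months, so the final assessment is month 12. Aim 1 lists among its secondary non-inferiority outcomes "dietary intake and physical activity at 6- and 12-months".

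The SAP's primary analysis is a linear mixed model of percent weight loss at 12 months that uses repeated weights. Its MVPA analysis is a repeated-measures GEE on whether the participant reaches 150 minutes per week. There the SAP states: "For participants missing MVPA at either follow-up timepoint will use a baseline observation carried forward approach". Its caloric-intake model is at 12 months only.

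**The concern.** A person who stops in month 2 and would attend both visits is, on the text, invited only to the second. Nothing explains why a voluntary leaver is offered less follow-up than a participant withdrawn for pregnancy.

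People who stop early are those whose 6-month values are most likely to differ from those of people who continue. Without the visit, three things happen:

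- The primary mixed model has no 6-month visit weight for them.
- Their 6-month MVPA status is set to the baseline category, although it could have been observed.
- The 6-month diet and activity outcomes named in Aim 1 are not collected for them.

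**Working it through.** **1. Who is affected.** Setting the texts side by side:

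| Route out of the intervention | 6-month visit | 12-month visit |
|---|---|---|
| Voluntary, before the 6-month visit | not offered | offered |
| Voluntary, after the 6-month visit | already due | offered |
| Pregnancy | offered | offered |
| Complete withdrawal | none | none |

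Only the first row has a gap that a change of wording could close.

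**2. The plan's own sample size.** Inputs from Justification of Sample Size: margin 2, SD 5.5, alpha 0.05 (sidedness not stated), power 90%, attrition 20%.

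- Normal approximation, one-sided 0.05: n = 2 × SD² × (1.645 + 1.282)² / margin² = 2 × 30.25 × 8.567 / 4 = 129.6, so 130 per arm.
- The noncentral-t calculation gives 131 (power 0.902), which matches the Protocol.
- 131 / 0.80 = 163.75, so 164 per arm and 328 in total, as stated.

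The first withdrawal choice keeps the 12-month weight, so these figures do not change.

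**3. How many.** The documents give no number who would stop before month 6 and accept the final assessment. Assuming 5% to 15% per arm: 0.05 × 164 = 8.2 and 0.15 × 164 = 24.6, or about 8 to 25 per arm.

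**4. Effect of carry-forward on one arm.** Let m be the share of the arm missing at 6 months. Let d be the true change from baseline, among those missing, in the proportion reaching 150 minutes per week. Carrying baseline forward shifts the arm's 6-month proportion by −m × d. For assumed d of 10 to 30 points:

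| m | Shift (percentage points) |
|---|---|
| 5% | −0.5 to −1.5 |
| 10% | −1.0 to −3.0 |
| 15% | −1.5 to −4.5 |

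**5. Effect on the contrast.** With G for Get Social and T for Traditional, the difference G − T moves by m_T × d_T − m_G × d_G.

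- Equal m and equal d: no movement.
- Equal d of 10 to 30 points, with m_T 10 points above m_G: 0.10 × 10 to 0.10 × 30 = +1 to +3 points, towards Get Social. The sign reverses if Get Social has the larger share missing.
- Equal m of 15%, with d_T 10 points above d_G: 0.15 × 10 = +1.5 points. The sign reverses if d_G is the larger.

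These are differences in crude proportions, not odds ratios from the GEE. The documents give no margin for this binary outcome (the Protocol's 9.2 minutes per day is for continuous MVPA), so the shifts cannot be set against a non-inferiority limit.

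**6. Primary model.** A leaver who attends month 12 supplies the primary value. One who then misses month 12 has no post-baseline visit weight. The Protocol's Intervention Phase and Measures table do provide for weights during the intervention, and the SAP does not say whether those enter the model.

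**The case against.** The strongest reply is that the wording is a fallback offer to people asking to leave. It does not prohibit a 6-month visit: the visits are scheduled without exception, and an assessment is not plainly an intervention contact. Protecting the primary 12-month visit at the price of an earlier one is a defensible trade. This stands in part. The loss comes from what is not offered, not from an explicit ban. But two matching passages name only the final assessment, so staff following them have no instruction to invite these people at month 6. The burden argument is met by keeping the final visit alone for those who decline more.

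Some stronger inferences are tempting but not supported:

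- **Early leavers contribute nothing to the primary analysis.** They keep the 12-month weight if they attend. Even if they do not, weights recorded before stopping may enter the model.
- **6-month diet would be analysed in completers only.** Neither analysis section contains a 6-month diet model, and the SAP says multiple imputation and other methods will be explored where more than 5% of a variable is missing. The diet consequence rests on Aim 1 alone.
- **Carry-forward necessarily pulls the arms together and so favours non-inferiority.** Similar stopping rates are not enough for that; leavers' true change must also differ by arm. With unequal rates the contrast can move either way.
- **The 20% attrition allowance (33 of 164) shows the scale.** It inflates the number evaluable for the 12-month primary outcome. Leavers who attend month 12 are not in that group.

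**Conclusion.** The point holds as a gap in follow-up for one group: voluntary leavers before month 6 who are willing to be assessed. The protocol already accepts off-intervention follow-up for pregnancy, so the omission looks avoidable. The firmest consequence is for 6-month MVPA, where an assumed value replaces one that could be observed.

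The 8 to 25 per arm rests on an assumed 5% to 15%, and on those people accepting a 6-month visit if asked; the number recovered would be smaller if some declined. The shifts of 1 to 3 points in the contrast need an assumed 10-point imbalance in missingness. Neither the size nor the direction of any bias can be settled from the documents. A reader might infer that the primary non-inferiority conclusion is at risk, but the texts do not show that. This is an inexpensive improvement to data collection.

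**What to change.** In the first withdrawal choice and in the Participant retention text, replace the offer of the final assessment with an offer of all remaining scheduled follow-up assessments (6 and 12 months), in line with the pregnancy provision. Keep the final assessment alone as the fallback for anyone who declines the 6-month visit. At 6 months, ask for the activity questionnaire as well as a measured weight, because weight alone would not recover MVPA. The dietary recalls are also needed if 6-month diet is to remain an Aim 1 outcome.

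The cost is one additional assessment for people who chose to stop, up to 150 minutes by the Protocol's Time Commitment table, plus its payment of $30 or $40. Economic Considerations makes payment conditional on completing every procedure, including all three recalls, so the text should say whether a shortened visit is paid.

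The Protocol describes waves 1 to 6 as already carried out, and the SAP is dated February 2021. If collection has finished, the sponsor can still report by arm how many lack 6-month data through this route, and add a sensitivity analysis aimed at the MVPA carry-forward. The SAP's general dropout sensitivity analyses are not tied to that imputation.

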2/26/2021

Statistical Analysis Plan

Study Title: Get Social: Randomized Trial of a Social Network Delivered Lifestyle Intervention

NCT02646618

Preliminary analysis

Baseline participant characteristics will be examined by condition. If groups differ on certain characteristics, these variables will be included as covariates in the primary analyses. Other preliminary analyses include assessing patterns of missing data, dropout rates, distributional properties of dependent measures, and correlations among outcome measures. A series of sensitivity analyses will be performed to examine the extent of potential bias by assuming the participants who dropped out are (i) missing completely at random (i.e., independent of the outcome), (ii) are responders to the intervention, or (iii) are non-responders to the intervention. Multiple imputation and other methods will be explore to address missing data for variables for which more than 5% of data are missing.

Primary non-inferiority outcome

We will model percent weight loss at 12 months using a linear mixed model, with percent weight loss as the dependent variable and study condition as the independent variable and accounting for repeated measures of weight. Test of the intervention condition indicator will provide a statistical test of the intervention effect and the estimated coefficient, along with the estimated confidence interval. This analytic approach aims to test whether the Get Social condition is not appreciably worse than (i.e., not inferior to) the traditional condition for percent weight loss at 12 months by our a priori inferiority margin of 2%. The effect estimates will reveal clinical non-inferiority of the Get Social condition if the confidence interval lies completely above $-\Delta$ or clinical non-inferiority of the traditional condition if the confidence interval lies completely below $+\Delta$, i.e., 2%.

Secondary non-inferiority outcomes

Linear multivariable models will be used to estimate change in daily caloric intake at 12 months; such models are reasonable given the target sample size and that changes in these outcomes are approximately normally distributed. We will examine the proportion of participants engaging in 150+ minutes/week of moderate/vigorous intensity physical activity (MVPA) using generalized estimating equations with a logit link function and incorporating repeated measures over time. For participants missing MVPA at either follow-up timepoint will use a baseline observation carried forward approach to impute their activity level (150+ vs <150 MVPA mins/week) at that timepoint. The distribution of secondary outcomes will be explored graphically and inform the primary outcome analysis; analyses will be modified as needed through transformation of the data.

Cost

We will calculate total intervention delivery costs per participant by treatment condition using time reported by intervention staff and convert to per-participant costs using national salary data from the Bureau of Labor Statistics. We will conduct sensitivity analyses to estimate a range of per-participant costs after varying the inputs (e.g., time spent conducting intervention, different intervention tasks, salary estimates). While we had originally aimed to examine costs for participants to participate in their respective intervention, we discovered methodologic challenges with collecting accurate and complete data from participants. As a result of what we learned, we have launched a separate study to develop methods for accurately collect participant time spent to participate in a social media delivered behavioral intervention. Without participant-level data, we are unable to conduct the analyses originally planned. Instead, we report the total intervention delivery costs per participant in both hours and dollars per participant for each of the two interventions.

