Aim 1: Efficacy. Our sample size estimates utilize methods developed specifically for non-inferiority trials.72 In a non-inferiority trial, the null hypothesis (H0) is that the new treatment is inferior to the standard treatment, and the alternative hypothesis (HA) is that the new treatment is not inferior to the standard treatment. "Not inferior to" is defined by the non-inferiority margin, δ . Here, we set $\delta = 2\%$, based on a clinically meaningful difference in average weight loss between the two treatment arms. This means that if the Get Social condition loses up to 2% less weight on average than the Traditional condition, we will consider the Get Social condition to be non-inferior to the Traditional condition. If the Get Social condition loses >2% less weight then it will be considered inferior to the Traditional condition. Thus, adequate power for clinical non-inferiority requires a sample size such that there is better than 90% probability that the lower limit of the confidence interval lies above $-\delta$, if the true effect size is zero or above. We estimated SD=5.5% based on our previous, fully powered randomized trial.28 With alpha=0.05, and δ =2%, we have 90% power to conclude that the Get Social condition is not inferior to the Traditional condition with 131 participants per arm. Accounting for 20% attrition, we will enroll 328 participants total (164 per arm). We considered adjusting the sample for intraclass correlation but previous research shows that weight loss does not cluster among members of weight loss treatment groups.1 We do not believe that the social influence in online groups will be stronger in the Get Social condition. Studies of social influence suggest that team-based activities or recruiting relatives or friends can lead to weight loss clustering but we will not be using such an approach.1 That said, we do believe that after the intervention, peer-to-peer engagement may continue for longer because participants will continue to have a channel by which to communicate with one another. They will also have the opportunity to collect additional social ties outside of the intervention which may be the source of social support, but this is likely to vary greatly across participants (not within treatment groups) and we do not have evidence that such ties will exert social influence of the magnitude of team-based activities and closer ties (i.e., relatives, friends). Secondary outcomes. For the secondary outcomes, we calculated the non-inferiority margins so that we have 90% power to detect given N=131 per arm, setting α=0.05, and using observed SDs from the literature. For change in kcal/day energy intake at 12 and 18 months, we have 90% to detect that Get Social is not inferior to the Traditional condition with a non-inferiority margin of 182 kcal/day with SD=500 kcal/day.28,56 For change in moderate-to-vigorous intensity physical activity minutes per day at 6 and 12 months, the non-inferiority margin is 9.2 minutes/day with SD=25 minutes/day. For percent weight loss at 12 months, the non-inferiority margin is 2.2% with SD=5.5%.28 If weight losses are more variable at 12 mos than 6 mos, the detectable non-inferiority margin is 3.0% with SD=8.0%.57 Power calculations were conducted using PROC POWER in SAS.73,74

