Participants will complete a telephone screening, an in-person baseline, and an online webinar (described above). Eligible participants will then be randomized to one of two 12-month weight loss interventions: online (Get Social) or in-person (Traditional). Follow-up assessments will occur at 6- and 12-months.

Randomization: Randomization will take place after the baseline procedures are complete once we've determined eligibility. Participants will be randomized to the Get Social or the Traditional condition. We will randomize 36-40 participants for each recruitment wave, for a goal of approximately 18 per condition. Participants will be randomized 1:1 to the two study conditions in randomly permuted blocks of size 4 and 6 using the ralloc program in Stata Randomization and will be stratified by gender (male vs. female) and baseline BMI (27.0-34.9 vs. 35.0-45.0). The randomization list was generated at the start of the study before randomization. The list is managed by the program director. Once a participant has been determined to be eligible, the program director will assign each participant to the next open assignment on the list. The program director will then tell the research assistant who will reach out to participants to inform them via e-mail of the condition assignment.

Orientation-Visits:

- Traditional participants: This in-person group will last 1 hour and will include training on The first session of the intervention will be extended from 1.5 hours to 2 hours in order to provide time for the orientation which will cover: -My Fitness Pal, an overview of their participation, and study goals. My Fitness Pal is an app that can be used to track diet and physical activity. It can be used on a computer or mobile app. Participants will receive their study goals for weight loss (1-2 lbs. per week), diet, and physical activity. The weight loss goal is approximately 7% weight loss over a 12 month period. This orientation may be completed on an individual in-person basis or phone for people unable to attend the group, though this option won't be encouraged. The weight loss goal is provided in the My Fitness Pal app. –The orientation group is led by the interventionist, a post-doctoral fellow, and a research assistant. and research assistants.

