Chronic Pain	Brief Pain Inventory ¹⁸	Х		X	Х	REDCap
Quality of Life	EQ-5D-3L ¹⁹	X		X	Х	REDCap
Contamination	Weight-loss related social media use*	X			X	REDCap
Social media use	Social Media Use*	Х		Х	Х	REDCap
Dietary recall	3 24hr recalls (ASA24- Automated Self- Administered) ²⁰	X (3)		X (3)	X (3)	Online
Social support for weight management	WMSI ²¹	X		X	X	REDCap
Measure time spent on Twitter	Phone or app tracking		X			REDCap
Group engagement on Twitter	Engagement in group		X	X	X	Twitter
Treatment receipt	Questions each week related to intervention*		X			REDCap
Intervention acceptability and burden	Questions given at 6m follow-up* and time spent data extraction from getsocial.com			X	X	REDCap
Interventionist Feedback (Interventionists only)	Interventionist Survey*			X		REDCap

* Investigator-derived items

Data Analysis: [For all studies, specify the analytic techniques the researcher will use to answer the study questions. Indicate the statistical procedures (e.g. specific descriptive or inferential tests) that will be used and why the procedures are appropriate. For qualitative data, specify the proposed analytic approaches.]

Preliminary analysis

Baseline participant characteristics will be examined by condition. If groups differ on certain characteristics, these variables will be included as covariates in the primary analyses. Other preliminary analyses include assessing patterns of missing data, dropout rates, distributional properties of dependent measures, and correlations among outcome measures. A series of sensitivity analyses will be performed to examine the extent of potential bias by assuming the participants who dropped out are (i) missing completely at random (i.e., independent of the outcome), (ii) are responders to the intervention, or (iii) are non-responders to the intervention. Multiple imputation to impute missing data will be used if more than 5% of data are missing.

Primary non-inferiority outcome

We will model percent weight loss at 12 months using a linear regression model framework, with percent weight loss as the dependent variable and study condition as the independent variable. Test of the intervention condition indicator will provide a statistical test of the intervention effect and the estimated coefficient, along with the

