estimated confidence interval. This analytic approach aims to test whether the Get Social condition is not appreciably worse than (i.e., not inferior to) the traditional condition by our a priori inferiority margin of 2%. The effect estimates will reveal clinical non-inferiority of the Get Social condition if the confidence interval lies completely above $-\Delta$ or clinical non-inferiority of the traditional condition if the confidence interval lies completely below $+\Delta$, i.e., 2%.

Secondary non-inferiority outcomes

Secondary non-inferiority outcomes (dietary intake and physical activity at 12 months) will be examined using the same approach as described for the primary outcome. Linear multivariable models will be used to estimate change in daily caloric intake at 12 months; such models are reasonable given the target sample size and that changes in these outcomes are approximately normally distributed. We anticipate using log transformation to estimate change in physical activity variables, given that physical activity data tends to be skewed. The distribution of secondary outcomes will be explored graphically and inform the primary outcome analysis; analyses will be modified as needed through transformation of the data.

Cost

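### The primary model leaves out gender and baseline BMI, the two stratification factors, and the imbalance-based covariate rule will almost never add them

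*SAP*

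**What the plan says.** **Design.** The Randomization paragraph of the protocol allocates 1:1 in permuted blocks of 4 and 6, and says allocation "will be stratified by gender (male vs. female) and baseline BMI (27.0-34.9 vs. 35.0-45.0"). That makes four strata.

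**Primary model.** The SAP (Primary non-inferiority outcome) specifies a linear mixed model and describes it as fitted "with percent weight loss as the dependent variable and study condition as the independent variable and accounting for repeated measures of weight". The protocol's version under Data Analysis is a linear regression "with percent weight loss as the dependent variable and study condition as the independent variable". Neither names gender, BMI or stratum.

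**Covariates.** The only route into the model is in the SAP's Preliminary analysis section, repeated in the protocol: "If groups differ on certain characteristics, these variables will be included as covariates in the primary analyses". No candidate list, test or threshold follows, and nothing is said about the stratification factors.

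**Transformation.** The last sentence of the SAP's section on secondary outcomes says that the distributions of those outcomes will "inform the primary outcome analysis; analyses will be modified as needed through transformation of the data". The protocol has the same wording: "The distribution of secondary outcomes will be explored graphically and inform the primary outcome analysis". The 2% margin is set in the protocol's sample size section, "based on a clinically meaningful difference in average weight loss between the two treatment arms", that is, on untransformed percent weight loss.

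**The concern.** An analysis should normally reflect the restrictions placed on the randomisation. If a factor is balanced by design and left out of the model, the outcome variation it explains stays in the residual. The reported standard error is then larger than the true sampling error of the treatment estimate. In a non-inferiority test this widens the interval and makes the lower limit harder to keep above −2%.

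The covariate rule cannot repair this. It looks for observed differences between arms, and stratified blocking removes them for exactly these two factors. The variables it can select are those out of balance by chance, and imbalance says nothing about whether a variable predicts weight loss. Because *differ* is undefined, the analyst also decides after seeing baseline data which differences count. The covariate set of the analysis that decides non-inferiority is therefore open.

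A smaller point of the same kind is that the transformation sentence, read literally, reaches the primary analysis. A transformed primary outcome would have no margin to be compared with.

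**Working it through.** **Inputs from the documents.** Margin 2, SD 5.5, true difference 0, alpha 0.05 (sidedness not stated), power 90%, 131 evaluable per arm, 20% attrition, 328 randomised; four strata, blocks of 4 and 6.

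**Inputs assumed.** R², the share of variance in 12-month percent weight loss explained by gender and BMI stratum, is not in the documents. It is shown from 0 to 0.20, with 0.03–0.10 as the working range.

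**1. The planned sample size.** n = 2 × 5.5² × (1.645 + 1.282)² / 2² = 130 per arm by the normal formula; the noncentral t version gives 131. One-sided 0.025 gives 159 (t: 160), so the plan's figure corresponds to one-sided 0.05 and no covariates. 131/0.80 = 163.75, hence 164 per arm and 328 in total. The plan's figure is reproduced.

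**2. Approximate gain from adjustment.** Power = Φ(2 / (5.5 × √(1 − R²) × √(2/131)) − z).

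| R² | Residual SD | Power, z = 1.645 | Power, z = 1.96 |
|---|---|---|---|
| 0 | 5.50 | 90.3% | 83.7% |
| 0.03 | 5.42 | 91.0% | 84.8% |
| 0.05 | 5.36 | 91.5% | 85.5% |
| 0.10 | 5.22 | 92.7% | 87.3% |

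These gains are upper figures, for the reason given in step 5.

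**3. Can the rule select a stratifier?** Reading *differ* as p < 0.05:

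- In 25,000 simulated trials with stratified blocks, neither factor ever differed at randomisation. The largest arm difference in the count of either factor was 6 people. Continuous BMI, and either factor among completers after random dropout, met the threshold in at most 0.02% of trials in any setting.
- In a separate set of 60,000 trials the rule picked a stratifier in 0.0%.
- With 10 independent irrelevant baseline variables (an assumed number), the chance of adjusting for at least one is 1 − 0.95¹⁰ = 40%.

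**4. Single 12-month outcome, simulated.** 5,000 trials per row, N = 328, 20% random dropout, 50% in each gender and 40% in the upper BMI stratum, one-sided 0.05. Type I error is taken at a true difference of −2.

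| R² | Mean SE, condition only / with strata | True SD of condition-only estimate | Type I error | Power |
|---|---|---|---|---|
| 0 | 0.679 / 0.679 | 0.687 | 5.7% / 5.6% | 89.8% / 89.8% |
| 0.05 | 0.679 / 0.662 | 0.666 | 4.9% / 5.0% | 90.1% / 91.1% |
| 0.10 | 0.680 / 0.646 | 0.638 | 3.9% / 4.5% | 91.7% / 93.3% |
| 0.20 | 0.680 / 0.608 | 0.627 | 3.8% / 4.9% | 91.8% / 94.5% |

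Monte Carlo error is about 0.3 to 0.4 points. At R² = 0 adjustment costs nothing visible.

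**5. Two-visit mixed model, simulated.** This is closer to the SAP. 10,000 trials per cell, unstructured covariance. Assumed: 30% men, 45% with BMI ≥ 35, correlation 0.8 between 6 and 12 months, and 10% and 20% missing at random at the two visits.

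| R² | Mean SE, condition only / rule / strata | Type I error, same order | Power with 90% CI, condition only → strata | Power with 95% CI, condition only → strata |
|---|---|---|---|---|
| 0.03 | 0.650 / 0.653 / 0.641 | 4.9 / 4.8 / 5.1% | 93.0 → 93.3% | 87.8 → 88.5% |
| 0.05 | 0.650 / 0.653 / 0.634 | 4.5 / 4.4 / 4.9% | 93.0 → 93.5% | 86.9 → 88.2% |
| 0.10 | 0.649 / 0.652 / 0.617 | 4.3 / 4.3 / 5.1% | 93.4 → 94.5% | 87.8 → 89.9% |

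At R² = 0.10 the true SD of the estimate is 0.624 condition-only and 0.621 with strata. The blocks have already delivered the precision, but the condition-only model reports 0.649. The loss is therefore an overstated standard error, not a noisier estimate.

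**The case against.** The strongest reply is that almost nothing is lost. The omission makes a non-inferiority claim slightly harder, never easier. The planned 90% power was computed without covariates and holds. On the alpha that reproduces the sample size, the simulated gain is about one point at most within the working range. That all stands.

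R² is also an assumption. Percent weight loss is already scaled to baseline weight, so gender and BMI may explain little of it. At R² = 0 the gain is nil, though so is the cost. The 40% figure follows from assuming ten variables and a p < 0.05 threshold, neither of which is in the SAP. Applied mechanically, the rule did no harm to type I error in simulation. What the simulation does not cover is discretionary choice of covariates, which the SAP's wording leaves open.

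Two further points are fair. The text does not forbid the stratifiers: a looser reading of *differ*, or unequal dropout, could admit one. And the SAP is dated 2/26/2021, with a cost section that already describes data-collection problems, so a change to the primary covariates might look late. But the two factors were fixed by the randomisation scheme before anyone was enrolled. Adding them is the choice least open to that charge, and less open to it than a rule applied to observed baseline differences.

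**Conclusion.** The point holds. The stratification factors are not in the primary model, and the only rule that could add them is one that stratified blocking all but prevents from doing so.

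The consequence is modest: a standard error about 1–5% too large and roughly 0.3 to 2 points of power, for R² between 0.03 and 0.10. Type I error is at or slightly below its nominal level. These sizes rest on the assumed R², stratum proportions, visit correlation and random dropout; the direction does not depend on them. The sample size of 328 need not change.

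This should be corrected, but it does not threaten the trial's validity. The main benefit is a primary covariate set fixed in advance in place of one left to chance imbalance.

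**What to change.** Replace the imbalance rule in the SAP with wording such as: *The primary mixed model will include gender and baseline BMI (continuous or by randomisation stratum) as fixed covariates, regardless of observed balance.* Keep any model adjusted for observed imbalances as a sensitivity analysis only, with its variables and threshold stated. If arm-level weight results had been seen before the change, say so and report the condition-only model beside it.

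Limit the transformation sentence to the secondary outcomes. State that untransformed percent weight loss is the scale on which the confidence interval is compared with −2%.

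Recruitment wave, which also carries site, may be added if wanted; no bias from leaving it out has been shown.

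The cost is SAP wording. The covariates use about 2 degrees of freedom, or about 10 of 262 evaluable participants if the nine waves are added (2 + 8). No new data are needed.
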